## 4 Study Objectives and Endpoints

### 4.1 Study Objectives

#### Protocol 1

**Specific Aim 1:** Utilizing a prospective randomized clinical trial study design, we will determine whether heat therapy improves **blood pressure** (both in clinic and ambulatory) better than dynamic aerobic exercise, the gold-standard non-pharmacological treatment of essential HTN. Specifically, we hypothesize that 30 sessions of passive heat therapy using hot water immersion over 8-10 weeks will improve blood pressure in HTN individuals to a greater extent than 30 sessions of exercise training over the same time period.

**Specific Aim 2:** We will determine whether heat therapy will improve biomarkers of arterial health and compare responses to exercise training. We hypothesize that 30 sessions of heat therapy will improve arterial stiffness in HTN to a greater extent than exercise. Furthermore, we hypothesize key clinical biomarkers of systemic inflammation and oxidative stress will be improved following heat therapy.

**Specific Aim 3:** In an exploratory aim, we will determine whether the acute decreases in blood pressure following an initial heat therapy session or exercise peak test predict the sustained reduction in resting blood pressures following heat therapy treatment or exercise training in HTN. These findings would provide significant predictive information beyond baseline resting blood pressures. We hypothesize that the reduction in blood pressure following acute stressors will be predictive of treatment effects on resting blood pressure.

#### Protocol 2

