**Table 1. Outcomes by Protocol and Aim**

Protocol 1			
Outcomes	Aim 1	Aim 2	Aim 3
Primary	Clinic systolic and diastolic pressures; Ambulatory systolic and diastolic pressures	Pulse Wave Velocity (measure of arterial stiffness)	Acute and chronic pressure reductions
Secondary	Heart rate; Cardiac output; Stroke volume; Total peripheral resistance; Secondary BP outcomes: waking, sleeping, dipper vs. non-dipper	Blood-borne biomarkers	
Protocol 2			
	Cognitive	Brain biomarkers of ADRD risk	
Primary Outcomes	Memory domain composite score*	Arterial transit time: mean perfusion in gray matter, mean perfusion in white matter	

\*average of age-corrected list-sorting and age-corrected picture sequence z-scores

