**Figure 1. Study Time Points**

RECRUIT
- Inactive men and women with HTN
SCREEN
- Multiple visits to assess blood pressure
PRE-TESTS
- Hemodynamic tests
- Muscle sympathetic nerve activity
- Biomarkers
- 24-h Ambulatory blood pressure
- VO 2 Peak Test
- Heat Test
ASSIGN
- Randomized to intervention group
INTERVENTION
- First 15 sessions
INTERIM-TESTS
- Hemodynamic tests
- 24-h Ambulatory blood pressure
- Biomarkers
INTERVENTION
- Last 15 sessions
POST-TESTS
- Hemodynamic tests
- Muscle sympathetic nerve activity
- Biomarkers
- 24-h Ambulatory blood pressure
- VO 2 Peak Test
- Heat Test

exercise training session. At the end of this 1st session, the subject will lay down for 1 hour of recovery, during which, we will continue to monitor core temperature, heart rate, and blood pressure every 5 min. NOTE: Subjects with contraindications for the ingestible core temp sensing pill will be encouraged to use a self-inserted rectal thermistor. If subject is contraindicated for the core temp pill and the rectal thermistor, their temperature will be monitored with a digital aural or oral thermometer.

**INTERIM-TESTS:** After half the intervention sessions have been completed, we will repeat our assessment of hemodynamic tests, 24-h urine collection and food/beverage log, 24-h ambulatory blood pressure and sleep/wake/activity log, and blood-based biomarkers related to cardiovascular health.

**POST-TESTS:** After the INTERVENTION, we will repeat high-resolution phenotyping of subjects which will include all the measures from the PRE-TESTS.

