**Table 3. Non-derived variables used in study assessments**

Variable	Aim/Primary or Secondary	Description
Protocol 1		
syst_bp_mean	Aim 1/Primary	Continuous; average of 3 systolic BP measurements collected in clinic at pre-, interim-, and post-intervention timepoints
diast_bp_mean	Aim 1/Primary	Clinic diastolic BP; Continuous; average of 3 diastolic BP measurements at 2 screening

		visits collected in clinic at pre-, interim-, and post-intervention timepoints
mean_rest_hr	Aim 1/Secondary	Continuous; average of 3 resting heart rate measurements collected in clinic at pre-, interim-, and post-intervention timepoints
Mean_qc	Aim 1/Secondary	Continuous; average of 3 cardiac output measurements collected in clinic at pre-, interim-, and post-intervention timepoints
Mean_qc	Aim 1/Secondary	Continuous; average of 3 cardiac output measurements collected in clinic at pre-, interim-, and post-intervention timepoints
Protocol 2		
mean_pcalib_gm	Brain biomarkers of ADRD/primary	Continuous; Mean perfusion calibration in gray matter, measure of arterial transit time
mean_pcalib_wm	Brain biomarkers of ADRD/primary	Continuous; Mean perfusion calibration in white matter measured by MRI, measure of arterial transit time

Note: means calculated in REDCap are not considered derived variables for the purposes of this table.

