**HEAT THERAPY VS EXERCISE TRAINING IN HYPERTENSION SAP**

dbp_dipper	Aim 1/Secondary	Categorical; non-dipper <10%, dipper ≥10% to <20%, and extreme dipper ≥20% change in diastolic BP at night calculated from ambulatory BP day and night averages
pwv	Aim 2/Primary	Continuous; average of three pulse wave velocity measurements collected at pre-, interim-, and post-intervention timepoints
il6_lg2	Aim 2/Secondary	Continuous; Biomarker IL-6 with the lower limit of detection (LLD) of 0.031 imputed for <LLD, log2 transformed for normalcy
crp_lg2	Aim 2/Secondary	Continuous; Biomarker CRP with the lower limit of detection (LLD) of 0.031 and upper LD (ULD) of 50 imputed for <LLD and >ULD, log2 transformed for normalcy
et1_lg2	Aim 2/Secondary	Continuous; Biomarker ET-1 with the lower limit of detection (LLD) of 0.031 imputed for <LLD, log2 transformed for normalcy
alb_lg2	Aim 2/Secondary	Continuous; Biomarker urine albumin with the lower limit of detection (LLD) of 0.031 imputed for <LLD, log2 transformed for normalcy
Supine.SBP.low	Aim 3/Primary	Continuous; average of three lowest consecutive supine systolic blood pressure measurements taken every 5 minutes for an hour post-intervention during supine recovery (for Heat Therapy: syst_bp55_ht_s1 to syst_bp110_ht_s1; for Exercise Training: for Heat Therapy: syst_bp55_ex_s1 to syst_bp110_ex_s1)
Supine.DBP.low	Aim 3/Primary	Continuous; average of three lowest consecutive supine systolic blood pressure measurements taken every 5 minutes for an hour post-intervention during supine recovery (for Heat Therapy: syst_bp55_ht_s1 to syst_bp110_ht_s1; for Exercise Training: for Heat Therapy: diast_bp55_ex_s1 to diast_bp110_ex_s1)
Supine.SBP.1.ch	Aim 3/Primary	Change from average pre-session resting SBP to Supine.SBP.low
Supine.DBP.1.ch	Aim 3/Primary	Change from average pre-session resting DBP to Supine.SBP.low
eGFR	Aim 1/Exploratory	eGFR was calculated using the CKD-EPI Creatinine-Cystatin Equation (2021) using the CKDEpi_RF.creat.cys function in the nephron R package and rounded to two decimal places
uacr	Aim 1/Exploratory	Urine albumin creatinine ratio (mg/g) was calculated by dividing urine albumin by urine creatinine/1000 rounded to 2 decimal places
Protocol 2		
cognitive_score	cognitive/Primary	Averaged z-scores (centered & divided by standard deviation) of age-corrected picture sequence score (age_cor_score)

		and age-corrected list-sorting score (list_age_cor_scpre)
--	--	--

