## 9 Efficacy Analyses

For primary analyses for Protocol 1 Aims 1, primary outcomes will be compared between groups (heat therapy vs exercise training) over time (within subject repeated measurements) using two-way repeated measures mixed model including an interaction between intervention group and timepoint with pre-defined contrasts. For Specific Aim 1, to test the hypothesis that heat therapy improves blood pressure (both in clinic and 24H ambulatory) better than dynamic aerobic exercise, the null hypothesis will be that the interaction between group and timepoint is equal to 0. For Aim 2, to determine whether heat therapy will improve biomarkers of arterial health (arterial stiffness & biomarkers of systemic

inflammation and oxidative stress) and compare responses to exercise training, the null hypothesis will be that the interaction between intervention group and timepoint is equal to 0. For Aims 1 and 2 exploratory analyses, ANCOVA will be performed for primary and secondary outcomes, with pretest values entered as a covariate and treatment condition specified as a fixed factor. Demographic and physiological variables (age, sex, BMI) and pre-intervention blood pressure will be added one at a time to the ANCOVAs to test for an interaction on treatment effects. For Aim 3, we will use ANCOVA models to determine the predictive potential of acute post-exercise hypotension response for chronic changes in blood pressure, with pretest values entered as a covariate and systolic and diastolic blood pressure specified as a fixed factor. Analyses will be performed on the Intention to Treat population. Additionally, change from pre- to post-intervention in ambulatory and in clinic systolic and diastolic pressure will be correlated with change from pre- to post first intervention session supine systolic and diastolic blood pressure by Pearson correlation.

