## 12 Quality Assurance of Statistical Programming

Final statistical analysis will be performed using R on an Oregon Health and Sciences encrypted computer with Windows operating system that is stored in a locked office. R packages to be utilized will include lme4, lmerTest, emmeans, Rmisc, and rstatix for statistical analyses; tidyverse, GGally, ggpubr for data visualization; table1, crosstable, flextable, sjPlot, and stargazer for table creation.

To provide high quality code that is understandable, and allows reproduction of the analysis the following points will be followed: At the start of any code file there will be a set of comments that give: the author; the date and time of writing; references to inputs and outputs; reference to any parent code file that runs the child code file.

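### The SAP never says which group-by-timepoint contrast decides Aim 1, and the null it states does not isolate the pre-to-post difference that the trial was sized on

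*SAP*

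**What the plan says.** SAP section 9 compares the Aim 1 primary outcomes with a two-way repeated-measures mixed model, "including an interaction between intervention group and timepoint with pre-defined contrasts". For Aim 1, "the null hypothesis will be that the interaction between group and timepoint is equal to 0". The same null is stated for Aim 2. Neither document lists the contrasts or says which is primary.

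The outcomes are measured at three visits:
- Clinic pressure is the "average of 3 systolic BP measurements collected in clinic at pre-, interim-, and post-intervention timepoints" (SAP Table 3, systolic; diastolic has the same visits).
- Ambulatory pressure is repeated at the interim tests: "we will repeat our assessment of hemodynamic tests, 24-h urine collection and food/beverage log, 24-h ambulatory blood pressure and sleep/wake/activity log" (SAP 5.1).
- Pulse wave velocity, the Aim 2 primary, is the "average of three pulse wave velocity measurements collected at pre-, interim-, and post-intervention timepoints" (SAP Table 4).

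Aim 1 has four primary outcomes: "Clinic systolic and diastolic pressures; Ambulatory systolic and diastolic pressures" (SAP Table 1). Its hypothesis concerns the full course: "30 sessions of passive heat therapy using hot water immersion over 8-10 weeks will improve blood pressure in HTN individuals to a greater extent" than exercise does (SAP 4.1). The sample size (SAP 6) uses the group difference in pre-to-post change and a two-sample t-test. The planned Table 2 (SAP 15) reports effects across timepoints without singling one out. SAP 7.5 disclaims control for multiple comparisons.

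**The concern.** An interaction null over three visits is false whenever the groups' profiles differ anywhere. Aim 1 asks something narrower: whether heat lowers pressure more than exercise after 30 sessions. A rejected interaction could come from a mid-course difference that has gone by the end, and an overall test carries no direction. The interaction test and the pre-to-post contrast come from one fitted model and can reach different verdicts. With no contrast named, either could be presented as the primary result.

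**Working it through.** **Inputs from the documents.** Difference 4.0 mmHg (the smallest scenario), SD 4.5 mmHg, alpha 0.05, 50 enrolled, 20% dropout (SAP 6); 40 completers (protocol section C, sample size paragraph). So there are 20 per arm after dropout, or 25 per arm with none.

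**Assumptions.** Two-sided tests, timepoint as a factor, compound symmetry, complete data, and 4.5 as the SD of change. SAP 6 does not label the SD, so step 6 takes the other reading. The interim effect is not given and is varied from 0 to 4 mmHg.

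**1. The plan's own figures.** 4.0/4.5 = 0.89 reproduces. The enrolment of 50 at 90% power does not: an exact two-sided t-test needs 28 per arm, so 56 completers and 56/0.8 = 70 enrolled. At 20 and 25 per arm its power is 78% and 87%. That gap is a separate matter; these values serve here as a benchmark.

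**2. Degrees of freedom.** (2 - 1) x (3 - 1) = 2 for the interaction; 1 for the pre-to-post contrast.

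**3. Power for a 4 mmHg post difference.** Residual variance = 4.5²/2 = 10.125. For group differences e = (0, interim, post), noncentrality = (n/2) x sum of (e - mean e)² / 10.125, on 2 and 2(2n - 2) df.
- e = (0, 2, 4): the sum is 8; at n = 20, 10 x 8/10.125 = 7.90.
- e = (0, 4, 4): the sum is 10.67; at n = 20, noncentrality is 10.53.
- Contrast: (n/2) x (4²/2)/10.125 = 7.90 at n = 20 and 9.88 at n = 25, on 1 df.

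| Interim difference (mmHg) | Interaction, 20 per arm | Interaction, 25 per arm |
|---|---|---|
| 0 or 4 | 82% | 90% |
| 1 or 3 | 73% | 83% |
| 2 | 69% | 80% |

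The same-model contrast has about 79% at 20 per arm and 88% at 25, whatever the interim effect.

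**4. Transient interim difference, none at post.** For e = (0, 2, 0), (0, 3, 0) and (0, 4, 0) the sums are 2.67, 6 and 10.67. Noncentralities at n = 20 are 2.63, 5.93 and 10.53. The interaction null is rejected in 28, 56 and 82% of trials (34, 67 and 90% at 25 per arm). The pre-to-post contrast rejects at its nominal 5%.

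**5. Disagreement and choice of test (simulation, 100,000 trials per setting).** For a 4 mmHg post difference at 20 per arm:
- Half the effect at interim: contrast alone significant in 11.0%, interaction alone in 1.1%.
- Full effect at interim: 4.7% and 7.5%.

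The total is about 12% either way, and 8-9% at 25 per arm. Under no effect the interaction rejects in 5.0% and the contrast alone in a further 2.5%, so 7.5% if either may be called primary. This last figure does not depend on the SD.

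**6. If 4.5 is the SD at a visit.** SD of change = 4.5 x sqrt(2(1 - rho)) = 4.50, 3.49 and 2.85 at pre-post correlation 0.5, 0.7 and 0.8. With n = 20 and half the effect at interim, both tests have noncentrality 7.90, 13.17 and 19.75. Interaction against contrast power is 69 v 79%, 90 v 95% and 98 v 99%. Disagreement is about 12%, 5% and 1%.

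**7. Baseline adjustment of the post contrast (SD of change 4.5).** Visit SD = 4.5/sqrt(2(1 - rho)) = 4.5, 5.8, 7.1 and 10.1 at correlation 0.5, 0.7, 0.8 and 0.9. Residual variance = visit SD² x (1 - rho²), allowing for chance baseline imbalance. Power is 88, 83, 81 and 79% at 20 per arm, against 78% for the change-score t-test; it is 94, 91, 89 and 88% at 25, against 87%.

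**The case against.** **The 2 degrees of freedom are inferred.** This stands. The SAP gives no degrees of freedom and does not say how timepoint is coded. The software list ("R packages to be utilized will include lme4, lmerTest, emmeans, Rmisc, and rstatix for statistical analyses") does not settle it, because emmeans serves contrasts as readily as overall tests. If the model is read through coefficients with pre as reference, the group-by-post coefficient already is the pre-to-post contrast. The open choice is then between the interim and post coefficients, with a false-positive rate of about 9% if either may count. A numeric time trend would give 1 df but would still not be the pre-to-post contrast. The ambiguity survives each reading, so the point rests on the undefined contrast rather than on the 2 df.

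**The intended comparison is clear, and reporting is open.** Largely fair. Aim 1 and the sample size both point to pre-to-post, and SAP 9 says full model results will be saved. A reader might infer that nothing restrains the choice, or that selective reporting is planned; the documents support neither. But an intention readable from other sections is not a stated decision rule, and section 9 states a different one.

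**The study is declared hypothesis-generating.** That excuses the absence of multiplicity adjustment. It does not explain naming primary outcomes, a directional hypothesis and 90% power without naming the deciding test.

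**The interaction test is not always weaker.** Correct. A reader might infer that the plan wastes power. It may, if the effect builds gradually, but the interaction test is about 3 points stronger if none or all of the effect is present at interim.

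**The exploratory ANCOVAs cover this.** They are labelled exploratory and apply to interim or post pressure, which again leaves two candidates.

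**Conclusion.** The point holds as a gap in specification with a real consequence: the stated Aim 1 null can be rejected without any pre-to-post difference, and the contrast that answers Aim 1 is not named. It applies to all four blood pressure primaries and to pulse wave velocity. It would be wrong to conclude that the mixed model is invalid or that its interaction test is generally inferior.

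The size is moderate. The transient-effect rejection rates and the 12% disagreement assume timepoint as a factor, compound symmetry, an SD of change of 4.5 and 20 per arm. Twenty per arm is the pessimistic end, since SAP 7.2.1 requires only one post-baseline assessment and the 20% dropout was set for the per-protocol analysis. Disagreement falls to 8-9% at 25 per arm and to about 1% if 4.5 is a visit SD with correlation 0.8. The 7.5% false-positive rate depends on neither SD reading. The change should be made; confidence is medium because the coding of timepoint and the meaning of the SD are unstated.

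**What to change.** In SAP 9, name the 1-df heat-minus-exercise difference in pre-to-post change, taken from the planned mixed model, as the primary test for each of the four Aim 1 blood pressure outcomes, and for pulse wave velocity in Aim 2. List the interim contrast and the overall interaction as supportive.

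As a refinement, estimate the contrast with baseline adjustment: the pre-test value as covariate with interim and post as outcomes, or baseline means constrained equal. SAP 9.1 already plans baseline-adjusted models as exploratory, so this is feasible. The gain is about 1 to 10 power points over the change-score t-test, depending on the pre-post correlation. Naming the contrast removes the ambiguity without it.

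Date the change and disclose whether unblinded data had been seen; SAP 8.2 and the past tense in parts of 9.1 suggest that analysis had begun. Still report the interaction test that section 9 states.

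The cost is a few lines of SAP text, one more model line if the refinement is adopted, and no new data. The downsides are a late change to the deciding test and, without baseline adjustment, a loss of about 3 points of power if none or all of the effect is present at interim (82 v 79% at 20 per arm; 90 v 88% at 25).

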Specific Aim 2: We will determine whether heat therapy will improve biomarkers of arterial health and compare responses to exercise training. We hypothesize that 30 sessions of heat therapy will improve arterial stiffness in HTN to a greater extent than exercise. Furthermore, we hypothesize key clinical biomarkers of systemic inflammation and oxidative stress will be improved following heat therapy.

Specific Aim 3: In an exploratory aim, we will determine whether the acute decreases in blood pressure following an initial heat therapy session or exercise peak test predict the sustained reduction in resting blood pressures following heat therapy treatment or exercise training in HTN. These findings would provide significant predictive information beyond baseline resting blood pressures. We hypothesize that the reduction in blood pressure following acute stressors will be predictive of treatment effects on resting blood pressure.

Protocol 2:

The overarching goal of this research is to determine whether 30 sessions of heat therapy or exercise training (performed by subjects in Protocol 1) improves cognitive function (using the NIH Toolbox: <http://www.nihtoolbox.org>) and MRI-based markers of aging and Alzheimer's risk (using specific MRI-based biomarkers and tests).

Subjects enrolled in Protocol 1 will be given the opportunity to participate in an additional protocol in which they will undergo biomarker testing for risk of ADRD before and after heat therapy or exercise training. Subjects will not be able to enroll in Protocol 2 without enrolling and participating in Protocol 1; this is required as Protocol 2 only adds some additional measurements for cognitive function and ADRD risk performed before and following the heat therapy and exercise interventions detailed in Protocol 1. Protocol 2 will include completing the NIH Toolbox for cognitive function, Pittsburgh Sleep Quality Index (PSQI), and MRI scans at the Lewis Center for Neuroimaging (LCNI).

Specific Aim 1: These studies in mid-life adults will determine if heat therapy can be used to improve cognitive aging and dementia risk, with potentially important clinical implications for the prevention of ADRD.

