## 6 Sample Size

**Projected effect sizes.** To estimate effect size for the primary outcome variables of systolic and diastolic blood pressures, we bracketed over several scenarios with varying pre- to post-intervention differences (i.e., with the fall in pressure following heat therapy being 4.0, 4.5, or 5.0 mmHg greater than following exercise training), and using a SD of 4.5 mmHg from our pilot work and published studies using similar interventions and approaches, which resulted in minimum hypothesized effect sizes of 0.89, 1.00, and 1.11 for Aim 1. For MSNA, we used a pre-intervention mean value of 39 $\pm$ 7 bursts/100beats based on our pilot data with 4 HTN subjects, and determined that a post-intervention mean value of 29 $\pm$ 7 b/100bts would represent a clinically significant change (of 10 b/100bts). Thus, for MSNA,  $d = 1.43$ .

Similarly, from our pilot work and our published studies using similar interventions and approaches, calculated effect sizes for  $\beta$ -stiffness  $d = 1.43$ , DAC  $d = 1.70$ , sympathetic baroreflex  $d = 1.33$ , FMD  $d = 2.55$ , carotid wall thickness  $d = 3.33$ , for Aim 2. Effect sizes for blood pressures were the lowest of our outcome variables; thus, powering for blood pressure will allow adequate power for numerous measurements giving us a global picture cardiovascular and autonomic health.

**Statistical power.** Our prospective power estimates based on a simpler model (two-sample RCT design, modeled as a two-sample t-test), to detect a minimum hypothesized effect size of 0.89 (which is smallest effect size of interest across outcome variables; power 90%;  $\alpha=0.05$ ), indicate the need to enroll 50 subjects (50:50 ratio of study groups; sample size assumes 20% dropout for the per-protocol analysis).

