For Protocol 2, where composite score cognitive function and brain biomarkers of ADRD risk outcomes were not collected at the interim timepoint, separate linear regressions will be performed for each outcome and predictor combination, where the post-intervention timepoint of the measure is the outcome, the pre-intervention measure of the outcome will be included as a covariate, and predictors will be intervention group in Aim 1 and 24H ambulatory systolic and diastolic blood pressure and arterial stiffness measures mean perfusion calibration in gray matter or white matter in Aim 2. Diagnostic plots and Cook's D of linear regressions will be assessed for influential outliers. If found and not improved through transformation, Robust regression using Huber weighting will be utilized instead.

Continuous outcomes will be transformed for normalcy prior to analysis. Methods used to check model assumptions will include checking for extreme outliers by visual inspection and Shapiro test and checking for homogeneity of variance by visual inspection and Levene's test. Full model results will be saved in an appendix or csv file, for possible use in planning future studies, meta-analysis and to enable replication of analysis.

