## 9.1 Exploratory Efficacy Analyses

In addition to Protocol 1 primary analyses, additional exploratory analysis will include analyses of covariance (ANCOVA) for each dependent variable of interest, in which pretest values will be entered as a covariate and treatment condition will be specified as a fixed factor in ANCOVA models. Demographic and physiological variables age, sex, and body mass index will be added one at a time to the ANCOVAs to test for an interaction on treatment effects using the following ANCOVA models with pre-intervention systolic or diastolic blood pressure (Pre SBP, Pre DBP) included as a continuous covariate. ANCOVA models based on the formula Interim or Post BP ~ Pre BP + <Interaction variable> + Intervention + <Interaction variable>\*Intervention and included the following terms in addition to Pre BP: Model 2, Pre BP\*Intervention; Model 3, Age + Age\*Intervention; Model 4, Sex + Sex\*Intervention interaction; Model 5, BMI + BMI\*Intervention interaction. SBP, DBP, age and body mass index (BMI) will all included in models as continuous variables with means estimated at selected values of interaction terms to illustrate how blood pressure measures did or did not vary by subgroup.

For Protocol 1 Aim 3, which is an exploratory aim, analyses of covariance (ANCOVA) models will be used to determine the predictive potential of acute responses for chronic changes in blood pressure. To test the association between acute decreases in blood pressure following an initial heat therapy session or exercise peak test and sustained reduction in resting blood pressures as measured by post-intervention ambulatory blood pressure, we will perform ANCOVA models with pre-session systolic or diastolic blood pressure (Pre-session SBP, Pre-session DBP) included as a continuous covariate. Pre-session BP is an average of three pre-session measurements and Post-session BP is lowest

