average of three consecutive readings taken every five minutes in the 55-110 minutes following the hour-long intervention. Group means for ambulatory blood pressure at the post-intervention timepoint will be estimated using the following formulas: Model 1, Post ambulatory BP ~ Pre-session BP + Intervention; Model 2, Post ambulatory BP ~ Pre-session BP + Intervention + Intervention\* Pre-session BP; Model 3, Post ambulatory BP ~ Pre-session BP + Intervention + Post-session BP + Intervention\* Post-session BP. BP measures will be included in models as continuous variables with means estimated at selected values of interaction terms to illustrate how blood pressure measures did or did not vary by subgroup. Additionally, exploratory correlations and PCA were performed among the following Project 1 variables: age, body mass index (BMI), HbA1c, total cholesterol (TC), Interleukin-6 (IL-6), C-reactive Protein (CRP), urine albumin to creatinine ratio (UACR), estimated glomerular filtration rate (eGFR), 24H ambulatory systolic and diastolic blood pressure (Amb. SBP, Amb. DBP), arterial stiffness measure pulse wave velocity (PWV), IPAQ long form continuous score MET-minutes/week (IPAQ), pre-first session resting SBP and DBP, maximum drop in supine SBP or DBP in the 55-110 minutes post-first heat or exercise session (Supine SBP or DBP drop), and total peripheral resistance (TPR), pulse wave velocity (PWV), renin, angiopoietin-2 (Ang2), endothelin-1 (Et1), and urine aldosterone.

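### The supplementary Aim 3 Pearson correlations make no allowance for arm, so a difference between heat and exercise alone can look like a link between acute and chronic blood pressure change

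*SAP*

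**What the plan says.** Aim 3 has this hypothesis in Protocol section B: "We hypothesize that the reduction in blood pressure following acute stressors will be predictive of treatment effects on resting blood pressure". The Protocol's description of the first session makes clear that the interest is in how individuals respond.

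The SAP plans two kinds of analysis for it.

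- **ANCOVA (SAP 9.1).** All three models contain the intervention. Model 3, the one that contains the acute response, begins "Post ambulatory BP ~ Pre-session BP + Intervention + Post-session BP" and adds the interaction of intervention with post-session pressure. The outcome is post-intervention ambulatory pressure.
- **Pearson correlation (SAP 9).** Pre-to-post change in ambulatory and in clinic pressure "will be correlated with change from pre- to post first intervention session supine systolic and diastolic blood pressure by Pearson correlation". The change summary in SAP 13 dates this addition to 22 May 2024. Neither place mentions arm.

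The status of the aim is explicit: "For Protocol 1 Aim 3, which is an exploratory aim". SAP 7.5 applies no multiplicity control.

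For Protocol 2, SAP 9 says that "separate linear regressions will be performed for each outcome and predictor combination", with the pre-intervention value of the outcome as covariate, and that "predictors will be intervention group in Aim 1 and 24H ambulatory systolic and diastolic blood pressure", together with the perfusion measures, in Aim 2. No timepoint is given for the Aim 2 predictors, and arm is not listed in those models.

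**The concern.** Aim 3 is a within-person question: does someone whose pressure falls more after the first session end up with a larger sustained fall? A correlation over all participants mixes that with a between-arm contrast. The trial is planned on the arms differing in chronic change. The acute stimuli are also different in kind, a hot bath against a cycling session, so the arms may differ in acute fall as well. If they do, the two clouds of points are displaced along both axes and the overall correlation is non-zero although each cloud is flat.

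If heat gives the larger fall on both axes, the spurious correlation is positive and reads as support for Aim 3. If exercise gives the larger acute fall and heat the larger chronic fall, it is negative and can hide a real within-arm relation. Either way the Pearson result and Model 3 could disagree for this reason alone, and the SAP does not say which would then govern.

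**Working it through.** **Inputs from the documents.**
- Chronic difference between arms, SAP 6: "the fall in pressure following heat therapy being 4.0, 4.5, or 5.0 mmHg greater than following exercise training".
- Spread, SAP 6: "using a SD of 4.5 mmHg from our pilot work", read here as the within-arm SD of change.
- Numbers: 50 enrolled 1:1 with 20% dropout, so 50 × 0.8 = 40 completers, which is the Protocol's completion figure.
- α = 0.05, taken as two-sided because sidedness is not stated.

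**The plan's own effect sizes reproduce.** 4.0/4.5 = 0.89, 4.5/4.5 = 1.00, 5.0/4.5 = 1.11. The documents give no figure for the correlations themselves.

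**Assumed.** The standardised acute difference between arms, dA, is not in the documents. It is varied from 0 to 2 SD. The within-arm correlation is set to zero.

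**Expected overall correlation from arm alone.** With 1:1 allocation and chronic difference dC,

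r = (dA·dC/4) / √[(1 + dA²/4)(1 + dC²/4)].

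For dC = 0.889 and dA = 1: r = 0.2222 / √(1.25 × 1.1975) = 0.2222 / 1.2235 = 0.18. 
For dA = 2: r = 0.4444 / √(2 × 1.1975) = 0.4444 / 1.5476 = 0.29. 
For dA = −1: r = −0.18.

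**False-positive rate.** 20,000 simulated trials per scenario, normal data, r tested two-sided at 5%. The adjusted column is the partial correlation given arm.

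| dA (assumed) | r from arm alone, dC = 0.89 | No arm term, N = 40 | Arm-adjusted, N = 40 | No arm term, N = 50 | No arm term, N = 40, dC = 1.11 |
|---|---|---|---|---|---|
| 0 | 0.00 | 5.1% | 5.4% | 5.0% | 4.9% |
| 0.5 | 0.10 | 9.5% | 4.8% | 10.2% | 11.3% |
| 1 | 0.18 | 20.2% | 5.0% | 24.3% | 27.6% |
| 1.5 | 0.24 | 34.2% | 5.0% | 42.0% | 46.8% |
| 2 | 0.29 | 45.9% | 4.9% | 54.9% | 62.4% |

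With dC = 0 the rate stays at about 5% for every dA. Both differences are needed.

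**What the ANCOVA covers.** Model 3 adjusts for arm, but its outcome is ambulatory pressure only, and its baseline term is pre-session pressure, not pre-intervention ambulatory pressure. SAP 9.1 therefore has no arm-adjusted acute-response model for clinic pressure, and none that relates acute change to chronic change.

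**Protocol 2 Aim 2.** 5,000 simulated trials per scenario with N = 40, an assumed pre-post correlation of 0.6, an arm effect of 0.89 SD on post-intervention blood pressure, no true association, and an assumed arm effect on the outcome of 0.5, 0.89 or 1.11 (in SDs after adjustment for its pre-value):

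| Predictor and model | 0.5 | 0.89 | 1.11 |
|---|---|---|---|
| Post-intervention BP, no arm | 9.1% | 16.3% | 23.6% |
| Post-intervention BP, with arm | 5.0% | 4.9% | 5.5% |
| Baseline BP, no arm | 5.0% | 4.7% | 4.9% |

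A baseline predictor is independent of arm by randomisation, so leaving arm out does not confound it.

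**The case against.** The strongest reply is that Aim 3 already has an arm-adjusted answer. The SAP names ANCOVA as the method for predictive potential, Model 3 includes arm and its interaction with the acute response, and the Pearson correlation is an addition within an exploratory aim of a study described as hypothesis-generating. This stands for ambulatory pressure, and a reader who inferred that Aim 3 has no analysis allowing for arm would be mistaken. It does not cover the clinic correlations or the change-on-change question. An exploratory label explains the absence of alpha control; it does not make an arm-driven correlation informative about individuals.

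A second reply is that the SAP is silent on arm and does not actually declare a pooled analysis. That is fair as a reading of intent. But a plain Pearson correlation with nothing said about arm, carried out as written, is one coefficient over all participants.

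A third reply is that the acute difference is unknown. This also stands. The 46% is the value at an assumed 2 SD, not a forecast, and at no acute difference there is no inflation.

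A reader might also extend the point to Protocol 2 and say that those regressions could falsely show acute response predicting chronic response. They contain no acute-response variable, so that cannot arise there. Nor do the documents establish that arm confounds them, because that depends on the unstated predictor timepoint and on an arm effect on memory or perfusion for which no figure is given.

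**Conclusion.** The concern holds for the supplementary Aim 3 Pearson correlations. At the planned d = 0.89 with 40 completers, the false-positive rate is about 5%, 10%, 20% or 46% for an assumed acute difference of 0, 0.5, 1 or 2 SD, against about 5% with arm adjusted. The chronic difference is the plan's own; the acute difference is an assumption. The exposure is greatest for the clinic-pressure correlations, which have no arm-adjusted counterpart. The change is worth making because the better statistic is almost free, but this does not undermine the aim as a whole.

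For Protocol 2 Aim 2 the firm finding is narrower and held with less confidence: the predictor's timepoint is missing. Protocol section H speaks of relating changes in cardiovascular markers to cognitive and imaging outcomes, which points towards post-intervention or change values, but SAP 9 does not say so.

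**What to change.** 1. In SAP 9, replace the plain Pearson correlations with partial correlations adjusted for arm, for ambulatory and clinic pressure alike, and report the two within-arm correlations beside them.
2. Name Model 3 in SAP 9.1 as the Aim 3 inference for ambulatory pressure, with the correlations as description.
3. In the Protocol 2 paragraph of SAP 9, state the timepoint of each Aim 2 predictor. Where it is a post-intervention or change value, add intervention group; for a post-intervention value, also add the predictor's pre-intervention value. Where it is a baseline value, arm is not needed to avoid confounding.

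The cost is SAP wording and 1 to 2 degrees of freedom per model. For the partial correlation at N = 40 this means 37 instead of 38. No new data are needed.
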